6.7. MEASUREMENTS

- Demographic variables: age, sex, weight, height, comorbidity (ASA grade).
- Variables related to the injury: subcapital fracture, pectrochanteric, subpectrochanteric or others.
- Variables related to the type of surgery: partial hip arthroplasty, endomedullary nailing or others. Duration of surgery.
- Variables related to the response:
 - Latency: evaluated by analgesic scales up to 10 minutes.
 - Analgesic scales: EVN, Algoplus and PAINAD at rest and in activity. They will be carried out upon the patient's arrival at the operating room, continuous until 10 minutes after the nerve block, in the sedation for the subarachnoid block, when they are discharged from the URPA, and at 6, 12, 24 h after the realization of the block, and end of effect after the realization of the block.
 - Need and rescue drugs: rescue analgesia will be scheduled for the hospitalization floor, in case it is necessary. The need, drug and time of administration regarding the realization of the blockade will be collected (Annex II).

6.8. ANESTHETIC PROTOCOL

- After giving informed consent to the patient or his guardian, the patient is monitored according to the usual standard (SEDAR Protocol, which includes ECG, TA, SatpO2).
- The ultrasound-guided block at the femoral level (PENG) is performed in the patient's transfer bed or table, depositing 20 cc of local anesthetic, with a 50-80 mm needle (depending on the anatomical characteristics) and a low-frequency probe. Next, a 50 mm needle and the high-frequency ultrasound probe will be used to block the NFCL by depositing 5 cc

of the same anesthetic, always without exceeding the maximum recommended dose for each drug. (See Annex I).

- Latency in the establishment of analgesia in the affected territory is explored, as well as an assessment of pain (Numerical Visual Scale and Algoplus).
- We proceed to the realization of the intradural spinal anesthesia, assessing again the pain that manifests. Subarachnoid blockade will always be performed with the same dose: 5 mg of Bupivacaine 0.5% hyperbaric with 10 µg of Fentanyl.
- After the surgical intervention, he will be transferred to the URPA (Post-Anesthetic Recovery Unit) and, subsequently, to the hospitalization floor when his situation allows it. At all times the constants, the analgesic variables and the treatments that you have needed will be recorded. (See Annex II).

6.9. JUSTIFICATION OF SAMPLE SIZE

Taking into account the Pharmacokinetics of both local anesthetics, and previous studies(28, 29), using the G*Power program, the sample size is calculated. We consider significant a difference in the duration of the blockade of at least 3 h, with a deviation of 50%. The security level or alpha error is 5%. The beta error is 20%. A total of 108 patients were obtained, 54 in each of the lines of intervention, assuming 10% of losses.

6.10. STATISTICAL ANALYSIS

A descriptive analysis of the variables collected will be carried out. Non-categorical ones shall be expressed as median +/- IQR (interquartile amplitude). Categorical variables shall be expressed as percentages or frequencies.

After performing the relevant normality tests (Kolmogorov-Smirnov or Shapiro-Wilk), the sample differences will be determined by t-Student or Mann-Whitney U tests. In the comparison of pain scales we will use the analysis of variance (ANOVA or Kruskal-Wallis).

The comparative analysis of the categorical variables will be carried out by means of Chi-square tests with cross tables.

The control of the possible intermediate and confusing variables will be carried out by means of Multiple Linear Regression Analysis.

The significance level will be, by default, 5% (p<0.05).

All calculations will be carried out with the statistical program SPSS[®] 25.0 for Mac.

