1.14. STUDY VARIABLES

A. Main endpoint: duration of nerve block (analgesic efficacy of the two local anesthetics).

B. Secondary variables:

1. analgesia latency
2. duration of analgesia
3. adverse effects of the drugs used
4. scores of the analgesic scales: EVN, Algoplus, PAINAD.

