6.11. ASSESSMENT OF EFFICACY

The main endpoint of the study's effectiveness will be the difference in the duration of the blockade.

6.12. POLICY REGARDING INTERMEDIATE ANALYSES AND CRITERIA FOR EARLY COMPLETION OF THE TRIAL.

This clinical trial may be stopped earlier than expected by the result of an interim analysis demonstrating greater than expected benefit or harm in any of the treatment arms. 1 formal internal efficacy and safety analysis will be carried out when 50% of the expected number of participants are reached. Poor study performance (e.g., slow patient recruitment, high rates of follow-up losses, or poor quality control) may be another cause of early study discontinuation.

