ANNEX III. DATA COLLECTION NOTEBOOK

Group	Levobupivacaine/Ropivacaine	
Hospital stay	In days	
Age	In years	
Sex	Female/Male	
Weight	In kg	
Size	In m	
Body Mass Index		
Type of Fracture	Subcapital/Petrochanteric/Subpетrochanteric/Other	
Type of Surgery	Partial athroplasty/Interlocking/Other	
Duration of Surgery		
On arrival at the operating room	EVN/Algoplus/Painad	
Latency time		
When sitting	EVN/Algoplus/Painad	
At Discharge of Resuscitation	EVN/Algoplus/Painad	
At 6 o'clock from the blockade	EVN/Algoplus/Painad	
At 12 o'clock of the blockade	EVN/Algoplus/Painad	
Within 24 hours of the blockade	EVN/Algoplus/Painad	
At the end of the blockade	EVN/Algoplus/Painad	
Analgesic rescue	Drug used	
Minutes to rescue	Time elapsed from lock to rescue	
Morphic equivalence	Equivalence in morphics of the rescue used	
Nausea and vomiting		
Toxicity	Toxicity developed by local anesthetics	
Delirium		
Infection	Clinically and analytically diagnosed	
Exitus		

BIBLIOGRAPHY

2. Tim JS Chesser DI, Antony Johansen, Alberto Belluati, Carlota Pari, Achile Contini, Stijn C Voeten, Johannes H Hageman, Kornelis J Ponsen, Nuria Montero-Fernández, Alberto Delgado-Martínez, Francisco Chana-Rodríguez Hip fractur systems-European experience. *OTA International.* 2020;3(1):1-6.
4. Fernández [name] M MJ, Olmos JM, [name]-[name] J, Hernández JL. Review of the incidence of hip fracture in Spain. *Rev Osteoporos Metab Miner.* 2015;7(4):115-20.

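### The primary endpoint, block duration, has no stated end event, no time field for it in the data collection notebook, and no rule for patients without an end time

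*Combined protocol and SAP*

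**What the plan says.** - **Endpoint.** Section 1.14 gives "Main endpoint: duration of nerve block (analgesic efficacy of the two local anesthetics". Section 6.11 says that the main endpoint of "effectiveness will be the difference in the duration of the blockade". Section 1.14 also lists duration of analgesia as a separate secondary variable and does not say how the two differ.
- **Measurement.** Section 6.7 schedules the pain scales "at 6, 12, 24 h after the realization of the block, and end of effect after the realization of the block". For rescue it adds: "The need, drug and time of administration regarding the realization of the blockade will be collected". Section 6.8 says: "At all times the constants, the analgesic variables and the treatments that you have needed will be recorded".
- **Notebook (Annex III).** The row "At the end of the blockade" lists the three scale scores. The row for minutes to rescue is explained as "Time elapsed from lock to rescue".
- **Rescue (Annex II, rescue treatment).** Analgesia is given on demand, elapsed time is noted, and follow-up is 48 h.
- **Analysis.** Section 6.10 says that "the sample differences will be determined by t-Student or Mann-Whitney U tests" and adds multiple linear regression for confounders. Section 6.6 only permits, and does not require, the use of data collected before withdrawal.

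**The concern.** Block duration is a time to an event, so it needs a start, an end, a recorded time for each, and a rule for patients whose end is not seen. The start is clear enough, because the duration items are counted from the block. Onset of analgesia also has a working rule in Annex I: the absence of pain on passive movement, explored for at most 10 minutes. The end has neither a rule nor a time field.

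Someone must therefore decide later what counts as the end and what to do with patients who have no value. The trial is open (section 4) and the research team does the analysis (section 10), so that decision could be taken with knowledge of allocation. The interim efficacy analysis at 50% of participants (section 6.12) needs the same undefined quantity.

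**Working it through.** **1. Passages side by side.**

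| Element | Onset of analgesia | End of block | First rescue |
|---|---|---|---|
| Event defined | Yes (Annex I) | No | Yes, drug given on demand |
| Assessment scheduled | Yes (6.7) | Yes (6.7) | Yes (6.7, Annex II) |
| Time field in Annex III | Yes, latency time | No, scores only | Yes, minutes to rescue |
| Declared as primary endpoint | No | Yes, as block duration | No |

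The event that is primary has no time field, and the event that has a time field is not declared primary. A patient who never demands rescue has no rescue time.

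**2. The plan's own sample size, to fix a scale.** Section 6.9 gives a 3 h difference, a deviation of 50%, alpha 5%, beta 20% and 54 per arm with 10% losses. It does not state the base of the 50% or whether the test is two-sided. Assume two-sided and SD = 50% of a mean of 10.5 h, that is 5.25 h:

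n per arm = 2 × (1.96 + 0.84)² × 5.25² / 3² ≈ 48.1, rounded up to 49; 49 × 1.1 = 53.9, rounded up to 54.

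This matches the stated 54, so means of 10.5 and 13.5 h are a workable illustration. They are not figures from the documents.

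**3. How much the missing rule matters if first rescue is the end event.** Assumptions: lognormal durations, means 10.5 and 13.5 h, coefficient of variation 50% in each arm, 49 per arm, 5,000 simulated trials per case. The never-rescued shares are assumed; the documents give none.

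| Never rescued (shorter / longer arm) | Mann-Whitney, ranked highest | Mann-Whitney, dropped | Verdicts differ |
|---|---|---|---|
| 2% / 2% | 69% | 71% | 8% of trials |
| 5% / 5% | 63% | 70% | 14% |
| 10% / 10% | 53% | 66% | 20% |
| 10% / 20% | 77% | 64% | 20% |

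If all are rescued, the mean difference is 2.99 h (restricted to 48 h) against 2.94 h with the few times beyond 48 h dropped, which is negligible. The direction is not fixed: dropping raises power when equal shares are never rescued and lowers it when more are unrescued in the longer-acting arm. A t-test with 48 h imposed does worst with equal shares: at 10% in both arms its power is about 20%, against 64% with those patients dropped.

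**4. A caution on the absolute powers.** A 50% coefficient of variation gives the longer arm an SD of 0.5 × 13.5 = 6.75 h, whereas 49 per arm was derived from 5.25 h. With every time observed, Mann-Whitney power is therefore about 72% here; with 5.25 h in both arms it is about 90%. The table shows the gap between rules. It does not measure the trial's power.

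**The case against.** The strongest reply is that the plan does foresee the moment in question. Section 6.7 schedules an assessment at the end of effect, section 6.8 has analgesic variables recorded throughout, and section 6.14.1 makes the electronic records a data source. Annex III is a terse list, and a time may well be written down in practice. This stands as far as it goes: a time may exist in the source notes. Without a definition, however, it need not mark the same event in each patient, and the notebook does not ask for it.

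Three stronger readings are tempting, and the documents do not support them.

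- A reader might infer that the end can be read only from rescue or from scales 6 to 12 h apart, too coarse for a 3 h target. The separate end-of-effect assessment in section 6.7 contradicts that.
- A reader might infer that the planned Mann-Whitney must give way to a survival test. On the assumptions above, ranking never-rescued patients highest gives 63%, 53% and 77% (5% in both arms, 10% in both, 10% vs 20%). The Breslow generalised Wilcoxon test gives 64%, 53% and 78%. Without early withdrawals the two are practically equivalent; only early withdrawals need censoring.
- A reader might infer that the time origin and withdrawal reasons are also missing. Sections 6.6 and 6.7 and Annex III largely cover them.

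It is also fair to say that if nearly everyone is rescued and rescue is the endpoint, the analysis rule hardly matters.

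**Conclusion.** The point holds for the definition, the time field and the missing rule, and it should be fixed before analysis. Followed as written, the notebook does not capture the primary endpoint unless rescue time is taken to stand for it, which the plan never says.

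This conclusion rests on the text alone. The size of the effect rests on assumed durations and assumed never-rescued shares. It ranges from negligible, when nearly all are rescued, to about 53% against 66% power with roughly one trial in five changing its verdict, when 10% per arm are never rescued. Confidence is high on the gap in definition and recording, and only conditional on how far the result would move.

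**What to change.** 1. The investigators name the event that ends the block and say how block duration differs from duration of analgesia.
2. Add an end-of-block time to the Annex III row, or designate minutes to rescue as the primary endpoint.
3. Reconcile the last timed scale at 24 h (section 6.7, Annex III) with the 48 h in sections 1.16 and 4 and Annex II (rescue treatment). Record the last time observed for each patient without an end time.
4. State in section 6.10 that all randomised patients are kept. Those with no end time by the end of follow-up are either ranked highest in the planned Mann-Whitney test, or censored there in a Kaplan-Meier and generalised Wilcoxon analysis. Early withdrawals and deaths are censored at that time, which calls for the censored-data form if there are any. Do not drop patients, and do not impose 48 h in a t-test. State how the regression treats them.

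The cost is protocol wording and about two notebook fields, with no new patients or visits. The downside is some loss of power against dropping patients if equal shares are never rescued (53% against 66% at an assumed 10% in both arms).

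### Pain scores taken before the block are recorded, but the pain-scale comparison in section 6.10 does not use them and the regression provision is unspecified, which gives up precision on secondary outcomes

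*Combined protocol and SAP*

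**What the plan says.** Section 6.7, which asks for each of the three scales both during activity and when resting, sets the schedule: "They will be carried out upon the patient's arrival at the operating room, continuous until 10 minutes after the nerve block". Later scores follow at the spinal puncture, at discharge from recovery, at 6, 12 and 24 hours, and when the effect ends. The data form in Annex III has a matching row, "On arrival at the operating room", for EVN, Algoplus and PAINAD.

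The scales are secondary variables in section 1.14: "scores of the analgesic scales: EVN, Algoplus, PAINAD". The primary endpoint is in section 6.11: "The main endpoint of the study's effectiveness will be the difference in the duration of the blockade".

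Section 6.10 has three sentences that bear on the point:

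- Continuous outcomes in general: "the sample differences will be determined by t-Student or Mann-Whitney U tests".
- Pain scales: "In the comparison of pain scales we will use the analysis of variance (ANOVA or Kruskal-Wallis").
- Adjustment: "The control of the possible intermediate and confusing variables will be carried out by means of Multiple Linear Regression Analysis".

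Allocation in section 6.5 is simple 1:1, with no stratification stated.

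**The concern.** A baseline on the same scale is usually the most useful covariate for a later score, and here it is already being collected. Neither named comparison is described as using it. Mann-Whitney and Kruskal-Wallis, as named, take no covariate. Any part of later pain that arrival pain explains therefore stays in the error term, and the pain-scale estimates are less precise than the data allow.

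The regression sentence does not settle the matter. It does not say which outcome is modelled, which covariates enter, or whether the result is primary or supportive. The trial is open (section 4) and the research team analyses the data (section 10), so covariates could be chosen after the results are seen. The sentence also covers intermediate variables. In the usual sense these lie between treatment and outcome, and adjusting for them can remove part of the effect the trial is meant to estimate.

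**Working it through.** **1. The plan's own figure.** The plan gives no precision figure for the pain scales. Its only sample-size figure is 108 (54 per arm, 10% losses), for duration (section 6.9). It cannot be firmly reproduced, because the deviation of 50% has no stated base and the sidedness is not given. Two readings, both two-sided 5% with 80% power:

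- SD = 50% of an assumed mean of 10.5 h = 5.25 h. n = 2 × (1.960 + 0.842)² × (5.25/3)² = 48.1, so 49 per arm. 49 × 1.1 = 53.9, so 54 per arm and 108 in total. This matches, but the 10.5 h is not in the documents.
- Standardised difference 0.5. n = 2 × (1.960 + 0.842)² / 0.5² = 62.8, so 63 per arm. 63 × 1.1 = 69.3, so 70 per arm and 140 in total. No match.

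The present point does not depend on which reading is right. It takes only the evaluable number from this section: 54 × 0.9 = 48.6, about 49 per arm.

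**2. Precision gained on a pain score.** Input: r, the within-arm correlation between the arrival score and the later score on the same scale. It is not in the documents, so a range is assumed.

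- Share of variance removed = r²
- Ratio of standard errors, adjusted to unadjusted = √(1 − r²)
- Equivalent number per arm = 49 / (1 − r²)
- Equivalent extra patients = 1 / (1 − r²) − 1

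| r (assumed) | Variance removed | SE ratio | Equivalent n per arm | Extra patients |
|---|---|---|---|---|
| 0.1 | 1% | 0.995 | 49.5 | 1% |
| 0.3 | 9% | 0.954 | 53.8 | 10% |
| 0.5 | 25% | 0.866 | 65.3 | 33% |
| 0.6 | 36% | 0.800 | 76.6 | 56% |

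**3. Chance imbalance at arrival.** In units of the arrival-score SD, the standard error of the difference between arms is √(2/49) = 0.202. The 95% range is ±1.96 × 0.202 = ±0.40 SD, and the chance of a gap above 0.25 SD is 22%. The gap does not enter the comparison whole: in outcome SDs, the shift in the unadjusted estimate is r × gap. A gap of 0.25 SD shifts it by 0.025 SD at r = 0.1, 0.075 SD at r = 0.3 and 0.125 SD at r = 0.5.

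**The case against.** The regression sentence could be meant to include arrival pain, and section 6.10 does not say that the ANOVA uses raw scores, or which time points enter it. That stands: the documents do not show that baseline is excluded, only that its use is unspecified.

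Arrival pain comes from an unfixed fracture, while later scores follow a block, a spinal anaesthetic and surgical fixation, so the correlation may be low. That also stands, which is why the range starts at 0.1, where the gain is negligible.

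A reader might infer that chance imbalance biases the trial. It does not. Under randomisation the unadjusted comparison is unbiased on average, and its type I error already allows for such imbalance. The issue is precision, and conditional bias in the particular sample drawn.

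A reader might also infer that the primary comparison loses power. The documents do not support this. Duration is a time, not a later reading of a pain scale, and nothing in the documents links it to arrival pain. Any power figure would need both an invented share of variance explained and an SD in hours that section 6.9 does not give.

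Finally, a linear model may fit poorly if bounded scores cluster near zero under a working block, and three scales in two conditions give six possible arrival scores. Both objections are fair and bear on how the change is worded.

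**Conclusion.** The point holds for the pain scales, as a matter of efficiency and prespecification rather than validity. A matching baseline is collected, the named pain-scale comparison does not use it, and the only adjustment provision is undefined and reaches post-treatment variables. The size is 1% to 36% of the variance, equal to 1% to 56% more patients, for an assumed correlation of 0.1 to 0.6 that has no source in the documents. The affected outcomes are secondary. No loss of power is shown for duration of block, and the planned unadjusted test of it is valid.

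**What to change.** In section 6.10:

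- Analyse each post-block pain score by ANCOVA, or by a mixed model across the scheduled time points, with arm and the arrival score on the same scale and in the same condition (rest or activity). If residuals are clearly non-normal, use a rank-based ANCOVA, or robust or bootstrap standard errors.
- For the regression, name the outcome, the covariates and the status (primary or supportive). Restrict covariates to pre-randomisation variables and drop intermediate ones from models of the treatment effect.
- For duration, keep the stated unadjusted test as primary. Add one supportive model with arm and a single named arrival score, and claim no gain in power from it.

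Two details need a line elsewhere. Section 6.5 does not say whether allocation comes before or after the arrival score; the score should be recorded before the scorer knows the arm, so that it is a true baseline in an open trial. The Annex III form shows no separate fields for rest and activity, although section 6.7 calls for both.

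The cost is a little more analysis work, those two clarifications, and no extra patients or visits. SPSS, the package already named, fits the linear model.

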3. HYPOTHESES AND OBJECTIVES

3.1. HYPOTHESIS:

Levobupivacaine has advantages over Ropivacaine in the combined blockade (PENG - pericapsular nerve group- and the femoral lateral cutaneous nerve -BNFCL-) in hip fractures of the elderly, since a better analgesic control, similar latency period, and a longer analgesic duration are obtained.

3.2. OBJECTIVES:

3.2.1. MAIN:

- To compare the analgesic efficacy of both local anaesthetics in the regional blockade of hip fracture surgery.

3.2.2. SECONDARY:

- To describe the behavior of this combined technique in hip fractures, establishing latency of onset and duration of analgesia.
- Describe the side effects derived from the described combined technique. To validate in our population, especially in patients with cognitive impairment, the usefulness of the analgesic scales chosen.

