ANNEX II.- RESCUE ANALGESIC TREATMENT:

- Review patient treatment in URPA and in the hospitalization floor. Do not administer scheduled analgesia unless the patient demands it, and for the same reason always leave a scheduled rescue . If necessary, notify the Resident of the Anesthesiology Guard (Virgen de la Vega Hospital building). Evaluate your pain and write down the elapsed time.
- **Paracetamol** 1 gr/ 6 h iv. If contraindication or allergy: Metamizol 2g/8 h iv. _
- If you need more analgesia and the 6 h has not passed:
- **Dexketoprofen** 50 mg iv/ 8 h.
- If contraindication to NSAIDs or pain persists:
- **Ondansetron** bolus 4mg iv and **Tramadol** infusion 200 mg iv + **Metamizol** 6 gr diluted in 500 cc S. Physiological to pass in 24 h (20ml/h). And discontinue Paracetamol, except in those allergic to Metamizole.
- Follow-up of the patient 48 h.

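### Section 6.10 lets the regression adjust for intermediate (possibly post-block) variables, and the between-arm comparison of pain scores leaves the arrival score unused

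*Combined protocol and SAP*

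**What the plan says.** All references are to the combined protocol and SAP.

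- **Regression (6.10).** "The control of the possible intermediate and confusing variables will be carried out by means of Multiple Linear Regression Analysis". No outcome, covariate list or timing rule follows.
- **Two-group differences (6.10).** A t test or Mann-Whitney U test, chosen after a normality test.
- **Pain scales (6.10).** "In the comparison of pain scales we will use the analysis of variance (ANOVA or Kruskal-Wallis"). No within-patient term, baseline adjustment or occasion is stated.
- **Main endpoint (6.11).** "The main endpoint of the study's effectiveness will be the difference in the duration of the blockade". Section 6.9 sizes the trial on the same quantity: "We consider significant a difference in the duration of the blockade of at least 3 h".
- **Hypothesis (3.1).** Levobupivacaine is expected to be superior, "since a better analgesic control, similar latency period, and a longer analgesic duration are obtained".
- **Data collected (6.7 and Annex III).** EVN, Algoplus and PAINAD are scored at "On arrival at the operating room", then on sitting, at discharge from resuscitation, at 6, 12 and 24 h, and at the end of the block. Latency is recorded, as are the rescue drug and its timing ("Time elapsed from lock to rescue").
- **Rescue (Annex II).** Given on demand: "Do not administer scheduled analgesia unless the patient demands it".

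**The concern.** In ordinary statistical usage an intermediate variable lies on the path from treatment to outcome. Several recorded variables fit that description: latency, post-block pain scores and rescue use. By the protocol's own hypothesis, the drug should improve analgesic control, so at least the post-block scores are expected to differ between arms because of the drug.

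Randomization protects the comparison of arms as randomized, and adjusting for pre-block variables keeps that protection. Adjusting for something the drug has changed does not. The drug coefficient then no longer estimates the total effect on duration: the part that runs through the intermediate is taken out. If the intermediate and duration also share causes, such as individual sensitivity to pain, a further bias enters. Because the regression sentence names no outcome, it can reach block duration. The report could then carry an adjusted result that disagrees with the valid unadjusted one.

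A smaller matter concerns the pain scores. An arrival score is available for each scale and is the natural covariate, yet the stated between-arm method does not use it. The method sentence also does not say how several scores from one patient enter the analysis.

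**Working it through.** **Inputs.** From Section 6.9: 3 h difference, alpha 5%, power 80%, 54 per arm including 10% losses. Evaluable per arm: 54 × 0.9 = 48.6, so 48 or 49.

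**The plan's sample size.** It cannot be reproduced, because Section 6.9 does not say what its 50% deviation is a percentage of. An SD of 1.5 h (50% of 3 h) needs 4 per arm. A standardized difference of 0.5 needs 64 per arm two-sided (72 with losses) or 51 one-sided (57 with losses). The SD is therefore solved backwards from a two-sided t test at 80% power:

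- 48 per arm: detectable difference 0.578 SD, so SD = 3/0.578 = 5.19 h.
- 49 per arm: detectable difference 0.572 SD, so SD = 3/0.572 = 5.25 h.

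An SD of 5.2 h is used below. It is an inference, not a figure from the documents.

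**Case 1: a true 3 h effect, part of it through the intermediate.** Assumptions: the drug shifts the intermediate M by 1 within-arm SD, a share s of the 3 h runs through M, the within-arm SD of duration is 5.2 h, and there are 49 per arm.

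- Adjusted effect = 3 × (1 − s).
- Residual SD = √(5.2² − (3s)²).
- A shift of 1 SD makes the squared correlation between arm and M equal to 0.25/1.25 = 0.2, so the variance inflation is 1/(1 − 0.2) = 1.25.
- Standard error = residual SD × √(2/49 × 1.25).

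| Share s | Adjusted effect (h) | Residual SD (h) | SE (h) | Effect/SE | Power |
|---|---|---|---|---|---|
| unadjusted | 3.00 | 5.20 | 1.05 | 2.86 | 81% |
| 25% | 2.25 | 5.15 | 1.16 | 1.94 | 48% |
| 50% | 1.50 | 4.98 | 1.12 | 1.33 | 26% |
| 75% | 0.75 | 4.69 | 1.06 | 0.71 | 11% |

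Simulation (4,000 trials per row) agrees: 2.2, 1.5 and 0.8 h, with power 47%, 26% and 10%, against about 80% unadjusted.

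**Case 2: no drug effect on duration.** Let the drug shift M by d SD, and let M and duration have within-arm correlation ρ. The adjusted drug coefficient then has bias −ρd in SD units.

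- |d| = 0.3, |ρ| = 0.3: 0.09 SD, or 0.09 × 5.2 = 0.5 h.
- |d| = 0.5, |ρ| = 0.5: 0.25 SD, or 0.25 × 5.2 = 1.3 h.

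In the direction the hypothesis implies (lower scores with levobupivacaine, lower scores with longer blocks), d and ρ are both negative, so the bias runs against levobupivacaine.

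**Arrival score.** ANCOVA multiplies the variance of the between-arm difference by 1 − ρ², where ρ is the correlation of the arrival and later scores. The documents give no such correlation. For an assumed 0.3 to 0.7 the variance falls by 9% to 49%. Because the scales are bounded, type I error was simulated for integer 0–10 scores with 40% at zero (49 per arm, 10,000 trials, correlations 0.3, 0.5 and 0.7). It was 5.1%, 5.3% and 5.0% for ANCOVA, and 5.0%, 5.3% and 5.0% for ANCOVA on ranks.

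**The case against.** The strongest reply is that the text is a rough translation. *Intermediate* stands beside *possible* and *confusing*, no covariate is named, and the authors may have meant only confounders. That the intermediates would be post-block variables is an interpretation of the word, not something the protocol says. This is fair, and it is why the point rests on what the sentence allows. It does not remove the need to fix the covariates: Section 4 describes the study as open, and Section 10 leaves the analysis to the research team.

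A reader might infer three stronger things that the documents do not support.

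- **That the primary analysis is biased.** Section 6.10 assigns group differences to a t or Mann-Whitney test, 6.11 makes the difference in duration the main endpoint, and 6.9 sizes the trial on it. The natural reading is an unadjusted primary comparison, which is valid.
- **That adjustment would produce false claims for levobupivacaine.** A false positive on duration needs a drug that relieves pain without prolonging the block, whereas Section 3.1 expects both effects. In the hypothesized direction the bias works against levobupivacaine. The more realistic harm is the shrinkage in Case 1.
- **That repeated pain scores will be pooled as independent.** The plan does not say so. Annex III has one entry per occasion, which suits separate tests. The ANOVA sentence might mean a repeated-measures analysis, or a comparison of the three scales, whose usefulness Section 3.2.2 sets out to validate.

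Nor is the arrival score wholly without a role: 6.10 promises a description of all variables, and the regression could include it. What stands is that the between-arm comparison of pain scores, as written, does not use it. Leaving it out costs precision, not validity. The sample size in 6.9 is based on duration, so no power figure for pain scores follows from it. The handling of post-rescue scores is missing detail on a secondary endpoint, and differential rescue would be visible in the recorded data.

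**Conclusion.** The point holds as one about the supportive regression and, to a lesser degree, the secondary pain-score comparison. Followed literally, Section 6.10 would have the regression condition on variables that the drug is expected to change, and the adjusted drug effect would then be attenuated or distorted. Under the assumptions of Case 1, 3 h becomes about 2.2 to 0.8 h and power drops from about 80% to about 47–10%. With no effect on duration, the bias is 0.09–0.25 SD.

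These sizes depend on assumed shifts, mediated shares and correlations, and the hours depend on an SD inferred from the sample size. The direction in Case 1 needs only that part of the benefit runs through the adjusted variable. Confidence is medium, because the intended meaning of *intermediate* is uncertain. The change is worth making before any data are analysed, including at the interim analysis at 50% of participants in Section 6.12.

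**What to change.** (a) In Section 6.10, delete *intermediate*. State that the unadjusted comparison of block duration is primary and that the regression is supportive. Limit its covariates to values fixed before the block: age, sex, fracture type and arrival pain score.

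(b) Compare pain scores between arms separately at each fixed occasion (sitting, discharge from resuscitation, 6, 12 and 24 h) by ANCOVA, with the arrival score on the same scale as covariate. Use ANCOVA on ranks as the non-parametric fallback. Do not pool occasions as independent observations. Describe the end-of-block score separately, since it falls at a different time in each patient. Section 6.7 asks for scores at rest and in activity, while Annex III as shown has one entry per scale and occasion. The text should therefore say which state is analysed and match the arrival score to it. If the ANOVA sentence was meant for comparing the three scales, say so and keep it for that purpose.

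(c) As a minor addition, show the share of patients rescued by each occasion beside the scores, using the recorded time to rescue.

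Cost: a few sentences of SAP wording and slightly more analysis work, all possible in SPSS. The covariates and the time to rescue are already in Annex III. The sample size and clinical procedures do not change.
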